### 8.1.2.6 PD/BIOMARKER EVALUATION IN BLOOD SAMPLES

Pre-treatment blood sample will be collected for biomarker evaluation and baseline analysis. The tests include genetic sequencing to obtain status of the germline mutations, liquid biopsy for tumor DNA or tumor secreted extra-cellular vesicles to identify biomarkers that will help predict drug efficacy.

## 8.1.3 NEURORADIOLOGY

Brain MRI scans (with and without contrast) will be performed per the Schedule of Activities.

### 8.1.4 RESPONSE ASSESSMENT IN NEURO-ONCOLOGY CRITERIA (RANO)

In Phase 0, RANO criteria will be used to confirm recurrence for eligibility criteria. In Expansion Phase, only those participants who have received at least one cycle of therapy and obtained an MRI in Expansion Phase will be considered evaluable. The Expansion Phase baseline MRI will be the first MRI taken post-operatively. Subsequent MRIs will be compared to the Expansion Phase baseline.

MRI scans will be evaluated using the criteria for response assessment incorporating MRI and clinical factors ([Chukwueke 2018](#)).

#### 8.1.4.1 EXPANSION COHORT EVALUATION OF TARGET LESIONS

##### Complete Response (CR)

Requires all of the following: complete disappearance of all enhancing measurable and nonmeasurable disease sustained for at least 4 weeks; no new lesions; stable or improved nonenhancing (T2/FLAIR) lesions; participants must be off corticosteroids (or on physiologic replacement doses only); and stable or improved clinically. Note: Participants with nonmeasurable disease only cannot have achieved CR; the best response possible is SD.

##### Partial Response (PR)

Requires all of the following:  $\geq 50\%$  decrease compared with baseline in the sum of products of perpendicular diameters of all measurable enhancing lesions sustained for at least 4 weeks; no progression of nonmeasurable disease; no new lesions; stable or improved nonenhancing (T2/FLAIR)

A Phase 0 Study of Infigratinib in Recurrent Glioblastoma Patients  
Protocol 2020-08

lesions on same or lower dose of corticosteroids compared with baseline scan; the corticosteroid dose at the time of scan evaluation.

**Stable Disease (SD)**

Requires all of the following: Does not qualify for CR, PR or progression; stable nonenhancing (T2/FLAIR) lesions on the same or lower dose of corticosteroids compared with baseline scan. In the event that the corticosteroid dose was increased for new symptoms and signs without confirmation of disease progression on neuroimaging, and subsequent follow-up imaging shows that this increase in corticosteroids was required because of disease progression, the last scan considered to show SD will be the scan obtained when the corticosteroid dose was equivalent to the baseline dose.

**Progressive Disease (PD)**

Defined by any of the following:  $\geq 25\%$  increase in the sum of the products of perpendicular diameters of enhancing lesions compared with the smallest tumor measurement obtained either at baseline (if no decrease) or best response on stable or increasing doses of corticosteroids†; significant increase in T2/FLAIR nonenhancing lesion on stable or increasing doses of corticosteroids compared with baseline scan or best response after initiation of therapy† not caused by comorbid events (e.g., radiation therapy, demyelination, ischemic injury, infection, seizures, postoperative changes or other treatment effects); any new lesion; clear clinical deterioration not attributable to other causes apart from the tumor (e.g., seizures, medication adverse effects, complications of therapy, cerebrovascular events, infection, etc.) or changes in corticosteroid dose; failure to return for evaluation as a result of death or deteriorating condition; or clear progression of nonmeasurable disease.

---

**8.1.4.2 EXPANSION COHORT EVALUATION OF NON-TARGET LESIONS**

**Complete Response (CR)**

Disappearance of all non-target lesions and normalization of tumor marker level. All lymph nodes must be non-pathological in size (< 10 mm short axis).

**Incomplete Response/Stable Disease (SD)**

Persistence of one or more non-target lesion(s) and/or maintenance of tumor marker level above the normal limits.

**Progressive Disease (PD)**

Appearance of one or more new lesions and/or unequivocal progression of existing non-target lesions.

---

**8.2 SAFETY AND OTHER ASSESSMENTS**

---

**8.2.1 DEMOGRAPHICS**

Demographic information (date of birth, gender, race) will be recorded at Screening.

---

**8.2.2 MEDICAL HISTORY**

Relevant medical history, including history of current disease, other pertinent history, and information regarding underlying diseases will be recorded at Screening.

---

**8.2.3 PHYSICAL EXAMINATION**

A Phase 0 Study of Infigratinib in Recurrent Glioblastoma Patients  
Protocol 2020-08

Physical examinations will include an examination as per standard of care and if available, will be obtained through the review of existing data in the medical record. The exam may include a review of general appearance, skin, neck (including thyroid), eyes, ears, nose, throat, lungs, heart, abdomen, lymph nodes, extremities, and a neurologic evaluation. The physical exam should be completed by appropriately licensed personnel as per institutional guidelines or as delegated by the Investigator.

---

#### 8.2.4 ABBREVIATED PHYSICAL AND NEUROLOGICAL EXAMINATION

An abbreviated physical and neurological exam will note any new findings or changes from baseline and should be completed by appropriately licensed personnel as per institutional guidelines or as delegated by the Investigator. May be obtained through the review of existing data in the medical record.

---

#### 8.2.5 OPHTHALMIC EXAMINATION

Ophthalmic examination will be assessed as per the assessment schedule (Section 1.2) and with any new onset of visual disturbance by an ophthalmologist and should include: visual acuity testing (including corrected distance acuity), slit lamp examination of the anterior eye segment, intraocular pressure (IOP), retinal OCT and dilated fundoscopy. Additional examinations such as specular microscopy and corneal pachymetry will be performed as clinically indicated. In addition, ophthalmic exams should be done as clinically indicated.

---

#### 8.2.6 PERFORMANCE STATUS

ECOG performance status will be assessed as per the assessment schedule (Section 1.2). More frequent examinations may be performed at the investigator's discretion, if medically indicated. (Appendix 12.1). ECOG should be completed by physician, nurse or other appropriately licensed personnel as delegated by the Investigator.

---

#### 8.2.7 VITAL SIGNS

Vital signs include body temperature, blood pressure, pulse, and respiration rate measurements and if available, may be obtained through the review of existing data in the medical record. If not available, the assessment should be completed per the Schedule of Activities. Blood pressure (systolic and diastolic) and pulse should be measured after the participant has been sitting for five minutes.

---

#### 8.2.8 HEIGHT AND WEIGHT

Height in centimeters (cm) and body weight (to the nearest 0.1 kilogram [kg] in indoor clothing, but without shoes) will be measured. Height will be measured at screening only. May be obtained through the review of existing data in the medical record.

---

#### 8.2.9 ELECTROCARDIOGRAM (ECG)

A standard 12-lead ECG will be obtained at Screening and Phase 0 Day 1 pre-dose. The single ECG that is obtained as routine care at the pre-surgical assessment will be collected. Additional single ECGs will be obtained as noted in the Schedule of Activities.

All ECGs should be obtained after the participant has rested in a supine position for at least 5 minutes on a machine that automatically calculates heart rate and determines intervals for PR, QRS, QC and QTc using the Fridericia formula.

## A Phase 0 Study of Infigratinib in Recurrent Glioblastoma Patients

Protocol 2020-08

Note: If the QTcF is >470 msec in the first pre-dose ECG, a total of 3 ECGs separated by at least 5 minutes should be performed. If the average of these 3 consecutive results for QTcF is ≤470 msec, the subject meets eligibility in this regard.

### 8.2.10 ECHOCARDIOGRAM (ECHO) OR MULTIGATED ACQUISITION (MUGA)

Cardiac imaging (ECHO or MUGA) should be performed if clinically indicated.

### 8.2.11 CRANIOTOMY

The craniotomy for tumor resection will be as clinically indicated. The date of surgery, intra-operative complications, location/site of sampling, the extent of tumor resected, and approximate percentage of tumor resected (if available) will be recorded in the CRF. Blood, tumor tissue, and CSF samples will be collected during the craniotomy per Sections 8.1.1 and 8.1.2. Additionally, radiographic images may be obtained during the surgical resection. Images will be de-identified.

If the participant undergoes repeat craniotomy for recurrence or progression of his/her brain tumor, IBTC will request samples from the resected tumor in order to evaluate for PK/PD assessments (see Section 8.1.1 and 8.1.2).

### 8.2.12 LABORATORY EVALUATIONS

Blood will be obtained and sent to the local laboratory for a CBC/hematology, blood chemistry, and pregnancy test as noted in the below table.

Table 9 Clinical laboratory parameters collection plan

Test Name	Test Category
Hematology	Hgb, platelets, white blood cells (WBC), red blood cells (RBC), differential (basophils, eosinophils, lymphocytes, monocytes, neutrophils [% or absolute])
Blood Chemistry	Albumin, amylase (or lipase), ALT, AST, bicarbonate, calcium, chloride, creatinine, total bilirubin, direct bilirubin (only if total bilirubin is ≥ grade 2), blood urea nitrogen (BUN), potassium, sodium, random or fasting glucose, alkaline phosphatase, total protein, magnesium, phosphorus Calculated or measured creatinine clearance
Urinalysis	Macroscopic panel (dipstick) (bilirubin, blood, glucose, ketones, WBC, pH, protein, specific gravity) Reflexive Microscopic panel (RBC, WBC, casts)
Pregnancy test	At screening visit, serum pregnancy test At subsequent cycles, urinary pregnancy test.
Coagulation	International normalized ratio (INR) and pro-thrombin time (PT) or Quick Test; activated partial thromboplastin time (PTT)

#### 8.2.12.1 HEMATOLOGY

Hematology assessments of the parameters listed in Table 9 will be tested as per the Schedule of Activities.

#### 8.2.12.2 CLINICAL CHEMISTRY

Blood chemistry assessments of the parameters listed in [Table 9](#) will be tested as per the Schedule of Activities.

#### 8.2.12.3 COAGULATION

International normalized ration (INR), prothrombin time (PT) and active partial thromboplastin time (aPPT) or Quick Test will be measured as listed in [Table 9](#) and per the Schedule of Activities.

#### 8.2.12.4 URINALYSIS

Dipstick measurements will be performed as per [Table 9](#) and according to the schedule of events. Any significant findings on dipstick will be followed up with microscopic evaluation as per Schedule of Activities.

#### 8.2.12.5 PREGNANCY AND ASSESSMENTS OF FERTILITY

Women who are determined to be of childbearing potential before the study will be tested. When non-childbearing potential status is determined during the study, pregnancy testing will not be completed. Women are considered post-menopausal if they have had 12 months of natural (spontaneous) amenorrhea with an appropriate clinical profile (e.g. age appropriate, history of vasomotor symptoms), and otherwise not of child bearing potential if they have had surgical bilateral oophorectomy (with or without hysterectomy) or tubal ligation at least six weeks ago. In the case of oophorectomy alone, only when the reproductive status of the woman has been confirmed by follow up hormone level assessment is she considered not of childbearing potential.

If a positive pregnancy test is performed in between study visits, the participants must immediately notify the investigator.

#### 8.2.13 PATIENT DERIVED XENOGRAFTS (PDX)

Participant-related tissue, cells and fluids from outpatient and inpatient sources will be collected by St. Joseph's Hospital and Medical Center (SJHMC); tissue will be processed and stored by the IBTC team according to standard collection, processing, and storage procedures and with Institution Biosafety Committee (IBC) approval. The IBTC team will prepare all tissue samples according to approved protocols and/or standard procedures (also called Working Instructions, WIs) for storage, development into cell lines, creation of patient-derived xenografts (PDXs) and/or preparation for histochemistry, as needed. Only SJHMC will be asked to collect tissue and provide to the IBTC.

See the Ivy Brain Tumor Center Laboratory Manual for details regarding collection, processing, packaging and shipment.

#### 8.2.14 ADVERSE EVENTS

Information regarding occurrence of adverse events will be captured throughout the study. Duration (start and stop dates and times), severity/grade, outcome, treatment and relation to study drug will be recorded on the CRF. See Section [8.3](#) for additional information.

### 8.3 ADVERSE EVENTS AND SERIOUS ADVERSE EVENTS

### 8.3.1 DEFINITION OF ADVERSE EVENTS (AE)

Adverse event means any untoward medical occurrence associated with the use of an intervention in humans, whether or not considered intervention-related (21 CFR 312.32 (a)). Adverse Events that are will be captured following first administration of study drug.

AEs include:

- Any deleterious change from the participant's baseline status, including an increase in the severity or frequency of a pre-existing abnormality or disorder;
- Concurrent illnesses;
- Injury or accidents;
- Subjective symptoms considered unfavorable by the reporter;
- Clinically significant physical examination, laboratory, imaging, or physiological testing abnormalities (abnormalities requiring treatment or a change in medication are AEs)
- Overdose

AEs do not include:

- Laboratory or test abnormalities that are not considered clinically significant
- Incidental findings on imaging that are not considered clinically significant
- Conditions for which a procedure was planned prior to signing the informed consent (e.g., elective knee replacement)
- Conditions present at baseline which have not worsened
- Hospitalization solely to complete procedures, or for social reasons such as respite care
- Cosmetic procedures
- Pregnancy without complications (see Section 8.3.9)
- Abnormal vital sign values that are not considered clinically significant; or, do not require medical intervention; or, interruption/change to study treatment; or, not accompanied by clinical symptoms.
- Events that are clearly consistent with the expected pattern of progression of the underlying disease (may be based on RANO or symptomatic deterioration).
- Events that are clearly related to surgical complications experienced as a result of the craniotomy and not related to study participation or the test article(s) should not be recorded as AEs. If there is any indication that the event may be related to study participation or the test article, the event should be recorded as an adverse event.

Cancer progression and cancer-related death are a study endpoint and will not be reported as an AE.

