### 9.4.2 ANALYSIS OF THE SECONDARY ENDPOINT(S)

PD Analysis: To compare pharmacodynamics biomarkers, paired archival, biopsy (if available) and surgical tissue will be examined. Once the percentage of individual biomarker positive cells was quantified, a paired t test will be used to compare log-transformed percent positive cells between archival, biopsy (if available) and surgical tissue at a 2-sided 5% level.

Safety Analyses: All adverse events will be tabulated according to the highest grade observed per patient for each event or category. Tabulations (n and %) will be produced for each of the following categories: Clinical laboratory abnormalities will be coded per CTCAE (Version 5.0)

- a. All treatment-emergent Adverse Events
- b. Treatment related Adverse Events (defined as those definitely, probably, or potentially related to treatment)
- c. Serious Adverse Events

---

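### The vital-sign exclusion in Section 8.3.1 joins its conditions with 'or' and so contradicts the inclusion list beside it, leaving treated or treatment-changing asymptomatic values open to being left out or recorded inconsistently

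*Combined protocol and SAP*

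**What the plan says.** Section 8.3.1 defines AEs by two lists.

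- **What AEs include.** One bullet covers any deleterious change from baseline, "including an increase in the severity or frequency of a pre-existing abnormality or disorder". Another covers "Clinically significant physical examination, laboratory, imaging, or physiological testing abnormalities (abnormalities requiring treatment or a change in medication are AEs").
- **What AEs do not include.** The vital-sign bullet removes abnormal readings described as "values that are not considered clinically significant; or, do not require medical intervention; or, interruption/change to study treatment; or, not accompanied by clinical symptoms". The matching bullet for laboratory and other tests has a single condition: "Laboratory or test abnormalities that are not considered clinically significant".

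Section 8.2.7 fixes the scope: "Vital signs include body temperature, blood pressure, pulse, and respiration rate measurements".

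Section 7.1 adds that a newly found abnormality of clinical relevance is to be reported as an AE. Section 8.3.4 says that a condition present at screening becomes an AE if it deteriorates during the study.

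Section 3 makes safety and tolerability a secondary endpoint of the Expansion Cohort, including drug-related toxicity, the number of AEs and treatment-emergent AEs. The analysis in Section 9.4.2 is "All adverse events will be tabulated according to the highest grade observed per patient for each event or category". Section 9.1 says that no separate SAP will be issued.

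**The concern.** An exclusion whose conditions are joined by 'or' takes effect as soon as one of them is met. The last condition is absence of symptoms. A raised blood pressure or slow pulse that the investigator judges significant, treats, or answers by interrupting infigratinib would therefore be excluded if the participant feels nothing. The inclusion list gives the opposite answer for the same event.

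The safety tables are built from recorded AEs. Section 9 specifies no on-treatment summary of vital signs, although the Schedule of Activities collects them, so an event not recorded as an AE would not appear in the planned safety tables by another route. With up to 3 sites, one could follow the inclusion bullet and another the exclusion, and the same event would be counted at one and not at the other.

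**Working it through.** No figure in the plan bears on this point, so there is none to reproduce. The check is of the logic of the wording.

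**Inputs.** Describe an abnormal vital sign by four yes/no features taken from the exclusion bullet: clinically significant (S), needs medical intervention (M), needs interruption or change of study treatment (C), symptomatic (Y). This gives 2^4 = 16 combinations.

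**The critical cases.** These are asymptomatic values that need intervention or a treatment change: Y = no, and M or C = yes. With S free there are 2 × 3 = 6 such combinations.

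**Parsing.** The third item in the bullet has no verb. It can be taken as a separate condition (no interruption or change needed), or merged with the second (neither intervention nor interruption or change needed). Both are tested, together with a version in which all conditions must hold.

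| Reading of the exclusion | Excluded when | Excluded of 16 | Not excluded | Of the 6 critical cases, excluded |
|---|---|---|---|---|
| Four separate conditions, 'or' | not S, or not M, or not C, or not Y | 15 | 1 | 6 |
| Items 2 and 3 merged, 'or' | not S, or (not M and not C), or not Y | 13 | 3 | 6 |
| All four joined by 'and' | not S and not M and not C and not Y | 1 | 15 | 0 |

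In the merged reading, the 3 combinations that survive are those with S and Y present and at least one of M and C (1 × 1 × 3). All 6 critical cases are excluded on either parsing of the present text, because the final 'or' removes every asymptomatic value.

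**Against the inclusion list.** Section 8.3.1 also says "abnormalities requiring treatment or a change in medication are AEs". Taken at its word, with a change to infigratinib counted as a change in medication, this makes all 6 critical cases AEs. The two lists therefore give opposite answers for all 6.

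**Which list prevails.** Nothing in Section 8.3.1 says. The inclusion bullet concerns "Clinically significant physical examination, laboratory, imaging, or physiological testing abnormalities". It does not name vital signs, though they fit naturally under examination or physiological testing. A site could treat the vital-sign bullet as the more specific rule and exclude, or could follow the inclusion bullet and Section 7.1 and record. Both are defensible from the text.

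The counts of 16 describe the logic only. The combinations are not equally likely: a value that needs treatment will usually also be judged significant.

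**The case against.** The strongest reply is that the protocol, read as a whole, already directs these events to be recorded. The inclusion list says so. Section 7.1 requires clinically relevant new findings to be reported as AEs, Section 8.3.4 covers deterioration of conditions present at screening, and in Table 3 a hold or reduction for a toxicity with no row of its own falls under other clinically significant AEs. The verbless third item also suggests a loosely drafted joint list, and a sensible investigator would probably read it that way.

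Much of this stands. A reader might infer from the exclusion bullet that such an event is definitely not an AE and is lost from the safety endpoint, with nothing elsewhere to recover it. The documents do not support that: several sections point towards recording. Concomitant medication records (Section 6.4) and dosing deviations in the CRF (Section 6.3) would also leave traces, although these do not feed the AE tables.

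A reader might also infer that a symptomatic, treated abnormality is excluded if study drug was not interrupted. That holds only if the third item is a separate condition. On the merged reading such an event, if clinically significant, is not excluded, and unfavourable symptoms are listed as AEs in their own right.

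The reply does not remove the contradiction. The other sections show that the exclusion bullet conflicts with the rest of the protocol, but none of them overrides it, and the final 'or' excludes asymptomatic values however the third item is read.

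**Conclusion.** The point holds as an internal contradiction in the AE definition. For an asymptomatic vital-sign abnormality that is treated, or that leads to interruption or change of infigratinib, Section 8.3.1 gives two opposite answers, and Section 7.1 sides with recording any such finding that is clinically relevant. The consequence is possible omission and possible inconsistency between sites in the AE and treatment-emergent AE tabulations.

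The size of the effect cannot be stated. The documents give no rate of vital-sign abnormalities, and the count of 15 or 13 excluded combinations out of 16 must not be read as a share of events. One participant left out would move a percentage by 1/20 = 5 points among 20 treated, or 1/10 = 10 points among about 10 in Expansion (50% of 20, Section 9.2). That is true of any missed event in a trial this small and does not measure this defect.

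The scope is vital signs only; laboratory and other test findings have their own exclusion, based on clinical significance alone. The endpoint is secondary and descriptive, and no hypothesis test depends on it. The conclusion assumes that vital signs fall within the inclusion bullet and that a change in medication includes a change to study drug. It is worth correcting because the rule is wrong as written and the correction is trivial.

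**What to change.** Reword the vital-sign bullet in Section 8.3.1 so that an abnormal value is excluded only when all four of the following hold together: it is judged not clinically significant, and it needs no medical intervention, and it leads to no interruption or change of study treatment, and it comes with no clinical symptoms. Giving each condition its own verb removes the parsing problem in the third item. Add one line stating that the inclusion rule prevails where the two lists conflict, and carry the same wording into the CRF completion guidance so that all sites apply it alike.

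The cost is one reworded sentence, one added line and a guidance update. The downside is that a few more low-impact AEs will be recorded. The change concerns what is recorded as an AE and does not alter dosing or clinical management.
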